11. Subject Population: Describe the characteristics of the participant population including the inclusion and exclusion criteria and the number of participants you plan to recruit:

A total of 40 clients admitted to the Opioid Diversion Program (ODP) will be enrolled for the T-CAP study and all will receive the T-CAP intervention. Since the sample will be drawn from the existing ODP, sociodemographic characteristics are expected to be similar to census demographics for the corresponding communities, with approximately 59% male, 88% white, and average age of 32. In addition, we expect approximately 40% will need mental health services as part of their treatment and 60% will need services for medical problems. The ODP screens out individuals who have a criminal record of violent offenses. While all current ODP clients have a recent history (within the past 12 months) of opioid use or other substance use, we will confirm this during the RA's administration of the TCU Drug Screen 5 and TCU Drug Screen 5—Opioid Supplement. If this process reveals that the individual does not have a recent history of opioid or substance use, they will be offered the opportunity to remain in the study but excluded from the primary analyses. Furthermore, individuals who are not willing to consent to granting research staff permission to access their police and treatment services records, and individuals who do not understand the informed consent (see appendix for the Informed Consent Comprehension Questions), will be excluded from the study. Individuals must demonstrate the ability to speak and understand English and be at least 18 years old to participate in this study. At the Informed Consent meeting, the RA will determine that these criteria are met.

[figure not shown]
12. Recruitment Procedure: Describe your recruitment strategies including how the potential participants will be approached and precautions that will be taken to minimize the possibility of undue influence or coercion. Include copies of the recruitment letters, leaflets, etc. in your submission.

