The standing video call arrangements will be entered into the tracking spreadsheet by the Coach and uploaded to TCU Box. The Coach will then alert the RA that the spreadsheet is ready for download. The RA will download and proceed to set up the 6 remaining telehealth sessions in the app scheduling feature. The RA will send a confirmation text or email to the participant with the schedule. The day prior to each of the 6 telehealth calls, the app will generate an automated reminder message about the upcoming telehealth call. We anticipate that there will be changes to the video call schedules, and participants will be advised to contact the RA for any schedule changes on video calls.

T-CAP Intervention. Coaching will be provided to the total study sample (N=40) by two licensed substance use treatment counselors, currently available through the Lake County Health Department. The Coach position requires professional training as a substance abuse counselor or equivalent (e.g., counselor with mental health credentials). Each Coach will be responsible for 20 participants during the 11-month implementation period. The study calls for two half-time Coaches, one to cover responsibilities in the event that one Coach is not available (e.g., due to vacation). In the event that one or both Coaches are unable to continue the study, replacements will be engaged for the project [the IBR has a strong collaborative relationship with several behavioral service providers in Lake and Cook Counties in Illinois.] Each participant will be assigned to only one of the Coaches for the duration of the intervention.

The 12-week telehealth intervention features 7 video calls on a smart phone, that will connect the participant with a Coach who will deliver the 3 components of the intervention: brief Motivational Interviewing (MI) sessions (see Appendix for MI scripts), recovery support, and assertive referrals to services that are intended to augment ODP substance use treatment or during post-treatment when there is an additional treatment need during recovery, as identified by the participant.

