MI telehealth sessions are scripted; session 1 introduces the participant to MI, sessions 2-6 continue the dialog aimed at motivating the participant to identify issues and solutions, and session 7 focus is on continuing recovery with a plan. Coaches will keep brief case notes on paper versions of the MI scripts, and this information will be entered into the Coach Procedural Fidelity Checklist in Qualtrics . Coaches will use the information to prepare for the upcoming telehealth session. In addition, 10% of MI sessions will be audio-recorded for further evaluation of the fidelity to the MI script content. For each Coach, this is 7 MI sessions during the 11-month study window. MI sessions will be randomly selected for recording by the Project Coordinator, who will add an entry in the caseload tracking spreadsheet, flagging the video call MI portion to be recorded. This information will be provided to the Coaches in the caseload tracking spreadsheet that is downloaded by the Coaches from TCU Box-our secure file-sharing method. Coaches will be provided with hand-held recorders to capture only the MI portion of the video call. Coaches will upload the recordings to TCU Box, for download by the Project Coordinator. Coaches will delete the recording off the recorder. MI recording will be evaluated by only the PI and Project Coordinator, who is trained in MI. Downloaded files will be kept on the IBR secure server for the duration of the study. When the project is completed, the audio files will be destroyed. No MI fidelity recordings will be stored in TCU Box.

Scheduled Telehealth Sessions. Planned telehealth sessions (N=7) are front-loaded during the 12-week intervention, with 1 telehealth MI each week for the first four weeks, MI 5 in week 6, MI 6 in week 8, and MI 7 in week 12. The MI portion of each session is designed to be a brief 15 minute activity. In addition to MI, the Coach and participant will update on relapse concerns and recovery progress, and identified treatment needs for medical or additional behavioral healthcare treatment. The Coach will assist the participant with arranging services/appointments with an *assertive referral*, which involves the Coach providing the participant with treatment options and contacting a prospective provider on behalf of the participant to arrange for an appointment. To support the Coaches with

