resources to complete the assertive referrals, the RA will maintain an Excel spreadsheet with area providers, available services, payment options, and contact information. Before the end of the telehealth session, the Coach will also confirm the next scheduled telehealth session with the participant. Overall, the telehealth sessions with MI and coaching support are expected to last up to 30 minutes. In addition to the Coach-initiated telehealth sessions, participants will be encouraged by the Coach to request additional telehealth sessions as needed. Participants will send a text message to the RA requesting a video call. The RA will reply via text message with scheduling options, based on availability of the Coach. We anticipate that special requests for video calls will be a response to a pressing issue that is weighing on the participant, so these calls will occur within the same day as the request whenever possible. The T-CAP research procedures for RA and Coach will be monitored with a monthly Procedural Fidelity Checklist (included in the Appendix).

Telehealth app data collection. There are two types of data from the T-CAP app: (1) function data (e.g., frequency of messaging, date/time of video calls and duration of calls), and (2) two telehealth satisfaction questions completed by participants at the end of each telehealth session (see appendix). Both data types will be available for download (from the cloud) to TCU Box. The data will be identified by the phone number. The phone number will be replaced with the Research ID by the Project Coordinator, so that no identifying information will be included in the analytic dataset.

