Aim 2: Evaluate the proposed T-CAP measures to assess their performance in gauging the impact of telehealth on initiation of in-person Substance Use (SU) treatment, short-term retention in referred SU treatment, and access to other appropriate treatment services (e.g., MAT). Our multidimensional approach includes data from self-report attendance and treatment engagement, self-report drug use, Coaches' advocate records on number of completed assertive referrals, and agency records from police and BH providers (including intake and during-program UA test results). In order to examine groups differences for intervention completers (C) vs non-completers (NC) (i.e., individuals who do not complete the 7 coaching video calls), group differences using t-tests and chi-square tests and we will estimate effect sizes needed for determining a sample size for a future R01 proposal. To assess potential assignment bias, we will test to see if there are baseline differences in demographics: participant race, gender, age and other demographic characteristics, as well as baseline measures of opioid use frequency and amount will be examined using chi-square and t-tests. Effect sizes will be computed for group differences on multiple outcomes (treatment initiation, retention, referrals to expanded SU service options, missed appointments). Service attendance records will be corroborated monthly with service provider records. Examinations of referrals to MAT and alternative pain management care between the C and NC groups, utilizing agency records data and the Coach tracking, will be conducted using a z-score to test differences in proportions of referral types. This will be calculated for all assertive referrals (resulting in scheduled appointments) collectively for a participant, as well as for different types of services.

Analyses of Secondary outcomes. We will examine differences between C and NC groups on several secondary outcomes. Analyses will typically involve t-tests, chi-square tests, and correlations. For example, we will use t-tests to assess differences between groups on the 3-month follow-up measures

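### Referrals are made in the coaching calls that define completers, so the completer versus non-completer referral effect size is partly built in and should not inform the R01 sample size

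*Combined protocol and SAP*

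**What the plan says.** Item 11 (Subject Population): "A total of 40 clients admitted to the Opioid Diversion Program (ODP) will be enrolled for the T-CAP study". All receive the intervention; there is no comparison arm.

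Study Procedures, T-CAP Intervention: the video calls are the channel "that will connect the participant with a Coach who will deliver the 3 components of the intervention". These are motivational interviewing, recovery support and assertive referrals.

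Study Procedures, Scheduled Telehealth Sessions: "Planned telehealth sessions (N=7) are front-loaded during the 12-week intervention", with four calls in weeks 1 to 4 and the rest in weeks 6, 8 and 12. After the interviewing portion and a review of needs, "The Coach will assist the participant with arranging services/appointments with an" assertive referral. The step that follows closes the same session: "Before the end of the telehealth session, the Coach will also confirm the next scheduled telehealth session with the participant". Further calls are possible, since "participants will be encouraged by the Coach to request additional telehealth sessions as needed".

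Item 14, Aim 2: non-completers are "individuals who do not complete the 7 coaching video calls". Referrals are one of four outcomes with a planned group effect size: "Effect sizes will be computed for group differences on multiple outcomes (treatment initiation, retention, referrals to expanded SU service options, missed appointments"). They are totalled per participant and by type of service. Effect sizes are wanted for sizing a future R01. A z-test is planned on proportions of referral types, without saying whether the denominator is participants or referrals. The only bias check is a comparison of baseline characteristics. No referral analysis takes account of the number of calls held.

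**The concern.** The grouping variable is whether all seven scheduled calls were held, and the outcome is something done during those calls. A completer had seven scheduled occasions for a referral; a non-completer had between none and six. A gap in referral totals can therefore appear between two groups with the same needs, served by a Coach who acts the same way on every call. This is separate from whether the groups are comparable at baseline, and the planned baseline comparison cannot detect it.

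Two uses are at risk. The contrast could be read as showing that completing T-CAP widens access to services, when part or all of it is exposure to the referral step. And an effect size of partly mechanical origin could go into planning the R01, which the protocol describes as a multi-site randomised trial.

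**Working it through.** The plan gives no effect size, referral rate, alpha, power or expected completion rate, so there is no figure to reproduce. The question is how large the referral contrast would be when nothing but the number of calls differs.

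**Inputs from the documents.** N = 40 (item 11). Completers hold 7 calls; non-completers hold k = 0 to 6 (item 14).

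**Assumptions.** A 20/20 split, two-sided 5% tests, and the referral models and call distributions below. On-request calls are ignored.

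**Model A: constant chance of a referral, r, at every call.** Referrals are Binomial(7, r) in completers and Binomial(k, r) in non-completers. With k uniform on 0 to 6 (mean 3, variance 4):

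- mean difference = 7r − 3r = 4r
- variance in completers = 7r(1 − r); in non-completers = 3r(1 − r) + 4r²
- d = 4r / √[(sum of the two variances)/2]

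For r = 0.2: 0.8 / √[(1.12 + 0.64)/2] = 0.8 / 0.938 = 0.85.

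| r | Mean referrals, completers vs non-completers | d | t-test rejection (simulated) | R01 n per arm at that d, 80% power |
|---|---|---|---|---|
| 0.1 | 0.70 vs 0.30 | 0.58 | 44% | 47 |
| 0.2 | 1.40 vs 0.60 | 0.85 | 75% | 22 |
| 0.3 | 2.10 vs 0.90 | 1.08 | 91% | 14 |

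A Poisson version with rates of 0.1 to 0.5 per call gives simulated d of about 0.57 to 1.19, the top of the range. If every non-completer holds 5 calls, d is 0.27 to 0.53 for r = 0.1 to 0.3; if every one holds 6, it is 0.13 to 0.26.

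**Model B: referral limited by need.** Each participant has a Poisson(1) number of needs, with the same distribution in both groups, and each unmet need is referred with probability q at each call. Expected referrals after k calls are m(k) = 1 − (1 − q)^k.

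For q = 0.5 and non-completers uniform on 3 to 6 calls:

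- completers: m(7) = 1 − 0.5⁷ = 0.992
- non-completers: 1 − (0.125 + 0.0625 + 0.0313 + 0.0156)/4 = 0.941
- variances 0.992 and 0.943 (for non-completers, the mean plus the variance of m(k)), so d = 0.051 / √[(0.992 + 0.943)/2] = 0.05

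| Non-completer calls | d at q = 0.3 | d at q = 0.5 | d at q = 0.7 |
|---|---|---|---|
| uniform 3 to 6 | 0.15 | 0.05 | 0.01 |
| uniform 1 to 6 | 0.29 | 0.16 | 0.07 |
| uniform 0 to 6 | 0.40 | 0.29 | 0.21 |

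Simulated t-test rejection runs from about 5% (the nominal level) to 24%.

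**Does a per-call rate remove it?** Under Model A, yes: the rate ratio is 1. Under Model B, no. With q = 0.5 and 3 to 6 calls, completers have 0.992/7 = 0.142 referrals per call and non-completers 0.941/4.5 = 0.209, a ratio of 0.68. Over the Model B scenarios in the table the ratio is 0.54 to 0.75. Completers look worse only because their later calls come after most needs have been met.

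**Share of referral types.** With equal type mix in both groups, a simulated z-test on each type's share of all referrals made showed a mean difference of about 0 and rejected about 5% of the time. Unequal call counts do not bias that comparison.

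**The case against.** The strongest reply is that this is the intervention working. Assertive referral is a delivered component, Aim 2 concerns access to services, and access is naturally counted per participant. More contact leading to more referrals is a real dose effect, and calling it an artefact presupposes a per-call question that the plan does not ask. This stands in part. The raw counts are a legitimate description of what was delivered. It does not rescue the effect size as evidence of impact, because a measure that tends to rise with the group definition cannot show what completion achieved.

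Second, a reader might take the Model A figures, d of 0.57 to 1.19 with 41% to 94% rejection, as the expected bias. The documents do not support that. The T-CAP Intervention and Scheduled Telehealth Sessions sections tie referrals to identified needs, and four of the seven calls fall in the first four weeks, so Model B is at least as plausible and its values are much smaller.

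Third, on-request calls are open to everyone, and the app data count unscheduled contacts. They may narrow the gap in opportunities. The plan does not use them in this comparison, so by how much is unknown.

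Fourth, referrals are one of four listed outcomes, and nothing says they will drive the R01 sample size. That is correct: the point concerns a stated possible use, not a certain one.

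**Conclusion.** The concern holds in a limited form. The per-participant referral contrast is partly built into the completer definition and, with equal needs and equal Coach behaviour per call, its expected value is zero or positive. The plausible size is d from about 0 to about 1.2; where in that range it falls depends on referral rates, call distributions and a group split that the documents do not give.

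Three stronger readings should be avoided:

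- That the observed difference must be positive. The statement is about expectation. One sample of 40 could show otherwise, and so could greater need among non-completers: under Model A, a per-call rate 7/k times that of completers (2.3 times at k = 3, 1.17 times at k = 6) would cancel it.
- That all planned referral analyses are affected. If the z-test compares each type's share of the referrals made, it is not.
- That the argument covers treatment initiation, retention or missed appointments. Those are not produced inside the calls and would need a separate argument.

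**What to change.** In item 14, Aim 2:

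1. Remove referrals from the completer versus non-completer effect sizes intended for R01 sizing.
2. Report referrals by group descriptively, next to the number of calls held (scheduled and on-request), and label the comparison as dose delivered, not as an effect of completion.
3. State the denominator of the referral-type z-test. Using referrals made keeps it free of this problem.
4. If a per-call rate is shown, present it as a sensitivity summary only, note that it is biased against completers when needs are met early, and list participants with no calls separately.
5. The share of identified needs that led to a referral may be used if Coaches record needs as a countable field. The Data from Coaches section mentions referrals, support services and case notes, but no such field.

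Items 1 to 4 are wording changes: the app already supplies call data and the Coach tracking file already records referrals. Item 5 adds one field to that file. The price is one fewer effect size for the R01.

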Baseline Survey Administration. After completing the Informed Consent, Demographics Form (e.g., age, gender, race/ethnicity, education level, previous use of telehealth), and Contact Information Form, the participant will receive the Qualtrics link via SMS text or email, to complete the Survey Baseline battery (included in the Appendix). The Qualtrics Survey Baseline assessment battery is completed on a participant's smart phone, hand-held tablet, or PC. The RA will provide the participant with their unique Research ID number, and this will be entered on the first screen by the participant. The Baseline assessment battery consists of forms available on our website (ibr.tcu.edu) and are widely used in substance abuse treatment settings and in our own research. The Baseline battery will also include a measure to gauge chronic pain. The Qualtrics Baseline battery, Demographics Form and Contact Information Form are expected to take up to 1 hour to complete, in addition to the time it takes to complete the Informed Consent administration (estimated at 20 minutes). Following completion of the Qualtrics Survey Baseline assessments, participants will receive an electronic gift card in the amount of \$80. At the end of the meeting, information on the next study meeting will be provided where participants will meet with their assigned Coach. Participants will receive instructions from the RA to (1) access the app on the phone equipment and (2) expect a text message from the Coach to schedule their first telehealth video call. The RA will explain the steps (listed below in "baseline procedures") that the Coach will use to schedule the first telehealth video call. The RA will further explain that the Coach will text message the participant the same day or next business day, except in cases where a participant joins the study on a Friday, in which case the Coach will text message the participant no later than the Monday that follows.

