Qualtrics Survey Mid-Intervention battery (T2). Participants will be contacted in week 5 by the RA to schedule a date and time to complete Mid-Intervention assessments battery in Qualtrics on a smart phone. The Mid-Intervention battery (and follow-up survey battery) repeats the baseline measures. To start the survey, The RA will confirm the unique Research ID number with each participant before sending the Qualtrics survey link, and this will be entered on the first Qualtrics screen. To start the survey, the participant will receive an SMS message with the Qualtrics survey link. At this timepoint in the study (and at follow-up), participants will also be asked to complete the Qualtrics version of the Telehealth Usability Questionnaire (TUQ), a 21-item measure rating the telehealth experience. The Qualtrics Survey Mid-Intervention assessment battery is expected to take 60 minutes to complete. Following completion of the battery, participants will receive an electronic \$40 gift card.

Follow-up surveys (T3). Following the same scheduling procedures used for the Mid-Intervention survey battery, participants will be contacted in week 11 to arrange the Follow-up Survey battery, expected to take 60 minutes to complete. Following completion of the assessments, participants will receive an electronic gift card in the amount of \$40. Following completion of the Qualtrics survey, the RA will contact the participants to thank each for their contributions to the project. All individuals will be invited to participate in an interview with a member of the research team. Our goal is to obtain feedback at the study closeout (Time 3) from a minimum of 6-8 participants. Interested participants may have the Participant Interview Informed Consent administered with the Media Authorization at this time, or the RA will schedule another meeting on a date and time that is convenient for the participant to complete the Informed Consent. The RA will FedEx the signed

documents overnight to the IBR research team and enter the information into the tracking spreadsheet, which is then uploaded to TCU Box for download by authorized project staff.

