of treatment motivation and psychosocial function from the TCU Client Evaluation of Self and Treatment (TCU CEST), a widely used form listed on the IBR web page. Validation of recent (last few days) self-reported opioid use will be compared with drug testing outcomes at each assessment time point using McNemar's test for change of state, as well as computing sensitivity and specificity statistics and the kappa statistic as a measure of agreement. We will compare self-report, as well as urinalysis (UA) results from agency drug screens between the two groups.

15. Potential Risks and Precautions to Reduce Risk: Indicate any physical, psychological, social, or privacy risk which the subject may incur. Risk(s) must be specified. Also describe what measures have been or will be taken to prevent and minimize each of the risks identified. If any deception is to be used, describe it in detail and the plans for debriefing.

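### The only stated TCU CEST analysis is an unadjusted 3-month t-test between completers and non-completers, so any difference present at entry carries into the result

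*Combined protocol and SAP*

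**What the plan says.** Randomisation has been removed, and all 40 participants receive T-CAP (study summary; section 11). Section 14, Aim 2, compares completers with non-completers, the latter being "individuals who do not complete the 7 coaching video calls". Under Analyses of Secondary outcomes, the plan says that methods will typically be t-tests, chi-square tests and correlations. It then gives an example: "we will use t-tests to assess differences between groups on the 3-month follow-up measures", where the measures cover motivation for treatment together with "psychosocial function from the TCU Client Evaluation of Self and Treatment (TCU CEST), a widely used form listed on the IBR web page". No other CEST analysis is stated.

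Aim 2 does plan a look at baseline: "To assess potential assignment bias, we will test to see if there are baseline differences in demographics". The clinical variables are added later in the same sentence: "as well as baseline measures of opioid use frequency and amount will be examined using chi-square and t-tests". CEST is not on that list, and no action follows if a difference is found.

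Whether CEST is measured at baseline has to be inferred. Baseline Survey Administration says: "The Baseline assessment battery consists of forms available on our website". The secondary-outcomes paragraph describes CEST as a form listed on the same institute's web page. The section on the mid-intervention battery (T2) says: "The Mid-Intervention battery (and follow-up survey battery) repeats the baseline measures". Together these make baseline CEST very likely. The appendix with the battery is not available to confirm it.

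**The concern.** Group membership is decided after entry. The steps for scheduling the first call let the participant accept or decline, so completing seven calls depends at least partly on the participant. Motivation at entry is a plausible reason for completing, and motivation is also one of the outcomes compared. If completers start higher and scores are correlated over time, they will tend to be higher at 3 months even if completing the calls changed nothing.

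The t-test answers one question validly: do the two groups differ at 3 months? It cannot say whether the difference arose during the 12 weeks. That distinction matters in this study. Aim 2 concerns measures for gauging the impact of telehealth, and the sessions themselves work on motivation: "sessions 2-6 continue the dialog aimed at motivating the participant to identify issues and solutions". A higher 3-month score in completers would readily be read as an effect of coaching.

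The stakes are limited. CEST is secondary and is not among the outcomes for which Aim 2 lists effect sizes.

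**Working it through.** The plan gives no figure to reproduce: no significance level, power, effect size, SD or completer split is stated.

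**Inputs.** From the documents: N = 40. Assumed: CEST standardised to SD 1; entry gap g = 0.5 SD; baseline-to-3-month correlation r = 0.4 to 0.7; completer/non-completer split 20/20 or 30/10; two-sided 5% test; all 40 followed up.

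**Unadjusted t-test.** With h = 1/n1 + 1/n2 (0.100 for 20/20; 0.133 for 30/10) and expected difference D, the noncentrality is D/√h on 38 df, and the rejection rate comes from the noncentral t distribution. For example, D = 0.20 at 20/20 gives 0.20/√0.100 = 0.632 and a rate of 9.5%.

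**Scenario 1: no group effect given baseline.** The t-test expects D = r × g, that is 0.4 × 0.5 = 0.20 to 0.7 × 0.5 = 0.35. ANCOVA expects 0.

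**Scenario 2: the entry gap simply persists.** The t-test expects D = g = 0.50. ANCOVA expects (1 − r) × g, that is 0.6 × 0.5 = 0.30 down to 0.3 × 0.5 = 0.15.

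| Scenario | Analysis | Expected difference (SD), r = 0.4 / 0.7 | Rejects, 20/20, r = 0.4 / 0.7 | Rejects, 30/10, r = 0.4 / 0.7 |
|---|---|---|---|---|
| 1 | t-test | 0.20 / 0.35 | 9.5% / 19.0% | 8.3% / 15.4% |
| 1 | ANCOVA | 0 / 0 | about 5% | about 5% |
| 2 | t-test | 0.50 / 0.50 | 33.8% / 33.8% | 26.6% / 26.6% |
| 2 | ANCOVA | 0.30 / 0.15 | about 16% / 9% | about 13% / 8% |

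ANCOVA rejection rates are from simulation with 40,000 replicates.

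**Sensitivity to the gap (scenario 1, t-test, r = 0.4 to 0.7).**
- Gap 0.2 SD: D = 0.08 to 0.14; rejection 5.7% to 7.2% (20/20) or 5.5% to 6.6% (30/10).
- Gap 0.8 SD: D = 0.32 to 0.56; rejection 16.7% to 40.8% (20/20) or 13.7% to 32.1% (30/10).

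**Precision.** The variance of the ANCOVA estimate relative to the t-test is (1 − r²) × [1 + (g² + h)/((N − 4) × h)].
- 20/20, g = 0.5: the bracket is 1 + 0.35/3.6 = 1.097, giving 0.84 × 1.097 = 0.922 and 0.51 × 1.097 = 0.560.
- 30/10, g = 0.5: the bracket is 1 + 0.383/4.8 = 1.080, giving 0.84 × 1.080 = 0.907 and 0.51 × 1.080 = 0.551.
- Unfavourable case, r = 0.3 and g = 0.8: 1.097 (20/20) and 1.057 (30/10).

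Adjustment therefore usually gains precision, with variance 8% to 45% lower, but it can lose 6% to 10% when r is low and the gap is large.

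**The case against.** - **No causal claim is made for CEST.** Aim 2 names treatment initiation, retention and access to services, and the secondary paragraph only proposes to examine group differences. This stands in part: the carried-over difference is misleading only if read as an effect. However, the expected-results statement before section 10 speaks of preliminary evidence of efficacy, so that reading is not far-fetched.
- **The sentence is only an example.** True, but it is the only CEST analysis written down. Aim 1 also plans to look at the characteristics of high and low participators, which could include CEST. It does not name CEST and plans no adjustment.
- **ANCOVA is not clearly the right model for non-randomised groups.** A comparison of change scores is unbiased in scenario 2. In scenario 1 it is off by −(1 − r) × g, that is −0.30 to −0.15 SD. Which scenario holds cannot be tested, so ANCOVA cannot be called correct. It is still closer than the stated t-test in both.
- **The numbers rest on assumptions.** They do. With a 0.2 SD gap the rejection rate is close to nominal. The scenarios also assume complete follow-up, which is optimistic for non-completers.
- **Non-completion may be outside the participant's control**, for instance after a lost phone or a change of coach. That is fair, but the groups remain non-randomised.

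**Conclusion.** The concern holds. For CEST, the stated comparison cannot separate a difference at entry from one that arose during the 12 weeks, and the planned baseline checks neither cover CEST nor lead to adjustment. Under an assumed 0.5 SD entry gap and r of 0.4 to 0.7, the carry-over is 0.20 to 0.35 SD, with rejection in about 8% to 19% of studies against a nominal 5%. If the gap simply persists, the figures are 0.50 SD and 27% to 34%. The true gap, correlation and split are unknown, so the actual size is unknown; a small gap would make it minor. The plan should be changed because the remedy is cheap, but for a secondary measure in a feasibility study the consequence is one of interpretation. The finding covers CEST only.

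**What to change.** First confirm that CEST is in the baseline battery. If it is:

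1. Replace the 3-month CEST t-test with an ANCOVA of 3-month CEST on baseline CEST and completion group, reporting the adjusted difference with a 95% confidence interval.
2. Add baseline CEST to the completer versus non-completer baseline comparison already planned under Aim 2, shown as standardised differences. Group means at both times also let the reader see change by group.
3. Report within-person CEST change from baseline for the whole cohort.

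Whether or not baseline CEST is available, state that the completer versus non-completer comparison is descriptive, because baseline adjustment does not remove self-selection.

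The cost is a few lines of text and a little more analysis, with no new data if baseline CEST is confirmed. Three limits remain: residual bias if the entry gap persists for reasons the baseline score does not capture, missing 3-month data in non-completers, and a small possible loss of precision if the correlation is low and the gap large.
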